### **10.3 Follow-up:**

- a. Prostatectomy: patients without evidence of  $^{68}\text{Ga}$ -RM2 PET positive nodal or metastatic disease noted on imaging will undergo radical prostatectomy. If a  $^{68}\text{Ga}$ -RM2 PET positive regional pelvic node is noted, the urologist will be informed of the location of the suspicious node and the patient will undergo prostatectomy with nodal dissection.
  - i. Patients with nodes seen on  $^{68}\text{Ga}$ -RM2 PET without positive nodes on pathology, will be rescanned with MRI or CT to determine if the suspicious node was thought to be removed. A  $^{68}\text{Ga}$ -RM2 PET may be repeated as well.
- b. If sites of  $^{68}\text{Ga}$ -RM2 PET positive osseous or distant metastatic lesions are noted, the urologist will be informed, and further evaluation including further imaging (bone scan,  $^{18}\text{F}$  NaF PET, CT or MRI cross section imaging) or targeted biopsy will be performed in order to restage the patient prior to the decision regarding whether or not a prostatectomy will be performed as per the responsible surgeon and standard of clinical care.
- c. The results of this research scan will be provided to the treating physician who may, at their discretion, decide to conduct further imaging scans and/or biopsies. The type and details of these additional scans are not specified, and are at the treating physician's discretion.
- d. Pathology: Specimens from prostatectomy will be evaluated for the presence of nodal metastasis. This will be reported on a per patient basis as positive or negative.
  - i. If possible, the presence of nodal disease on a per region basis (inguinal, left/right obturator, external and internal iliac, paraaortic nodal regions) should be performed. This data will be grouped for subanalysis.
  - ii. The number of nodes counted on pathology will also be recorded.

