### **10.4 Statistical analysis:**

- a. Sample size: 90 patients in total. The power analysis is based on the comparison of sensitivity between conventional imaging and  $^{68}\text{Ga}$ -RM2 PET.
  - i. 30% of intermediate to high-risk patients have nodal metastases at prostatectomy.

- ii. Conventional imaging has a 45% detection sensitivity for nodal metastases on a per patient basis (2).
  - iii.  $^{68}\text{Ga}$ -RM2 PET has a 60% detection sensitivity for nodal metastases on a per patient basis.
- b. Statistical analysis: The sensitivity, specificity, positive and negative predictive value of  $^{68}\text{Ga}$ -RM2 PET for the detection on a per patient basis will be determined using the below criteria:
  - i. True positive patient:
    - 1.  $^{68}\text{Ga}$ -RM2 PET positive for regional nodes; pathology at prostatectomy positive for regional nodes.
    - 2.  $^{68}\text{Ga}$ -RM2 PET positive for regional nodes, pathology negative for regional nodes, imaging after prostatectomy demonstrates node was not removed at surgery, and follow-up biopsy or imaging demonstrates presence of nodal disease.
      - a. Criteria for positive node on follow-up imaging: imaging within 3-12 months, the node decreases by more than 30% (for patients undergoing systemic treatment or focal therapy at this site) or increase by more than 20% in short axis diameter in the absence of treatment (with a minimum of 3 mm in change in size).
  - ii. True negative patient:
    - 1.  $^{68}\text{Ga}$ -RM2 PET negative for regional nodes; pathology at prostatectomy negative for regional nodes.
  - iii. False positive patient:
    - 1.  $^{68}\text{Ga}$ -RM2 PET positive for regional nodes, pathology at prostatectomy is negative, and imaging after prostatectomy demonstrates that node is no longer present.
  - iv. False negative patient:
    - 1.  $^{68}\text{Ga}$ -RM2 PET negative for regional nodes, but pathology at prostatectomy is positive.
  - v. Non-evaluable:
    - 1.  $^{68}\text{Ga}$ -RM2 PET positive for regional nodes, pathology negative for regional nodes, imaging after prostatectomy demonstrates node was not removed at surgery, and no definitive follow-up is available.
    - 2. Patients with extrapelvic nodal metastases will not be included in this analysis if patients do not undergo prostatectomy.

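### Section 10.4b: a PET-positive node shown to persist after surgery, with negative pathology, can count for PET but not against it, so specificity is unchanged or overstated, and PPV is overstated when the lost patients are benign

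*Combined protocol and SAP*

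**What the plan says.** Section 10.1.1 makes per-patient sensitivity, specificity, PPV and NPV the primary endpoint, with surgical pathology as the comparator. Section 10.4b then sorts PET-positive, pathology-negative patients by what later imaging shows of the node:

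- **False positive (b.iii.1):** "pathology at prostatectomy is negative, and imaging after prostatectomy demonstrates that node is no longer present".
- **True positive (b.i.2):** "imaging after prostatectomy demonstrates node was not removed at surgery, and follow-up biopsy or imaging demonstrates presence of nodal disease".
- **Non-evaluable (b.v.1):** "imaging after prostatectomy demonstrates node was not removed at surgery, and no definitive follow-up is available".

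The only imaging standard given is for disease. It opens "Criteria for positive node on follow-up imaging: imaging within 3-12 months" and asks for shrinkage of more than 30% in treated patients, or growth of more than 20% (at least 3 mm) in untreated ones. There is no matching standard for a benign node.

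Retained nodes are foreseen. Under Section 10.3a.i, patients with PET-positive nodes "without positive nodes on pathology, will be rescanned with MRI or CT to determine if the suspicious node was thought to be removed", with no time stated for the rescan. Section 10.3a also makes retention less likely: "the urologist will be informed of the location of the suspicious node and the patient will undergo prostatectomy with nodal dissection".

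**The concern.** One outcome is missing: node not removed, and definitive follow-up shows it to be benign. It is not b.iii.1, because the node is still there. It is not b.i.2, because no disease was shown. On its plain wording it is not b.v.1 either, because definitive follow-up exists. The text does not expressly exclude this patient, but it gives no way to score PET as wrong.

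Specificity and PPV are two of the four primary measures, and a real false positive of this kind enters neither. Without a rule, someone must also decide how to classify the patient after the PET result is known.

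**Working it through.** **Inputs from Section 10.4a.** N = 90 and prevalence 30%, so 0.30 x 90 = 27 pathology-positive and 63 pathology-negative patients. PET sensitivity is 60%, so 0.60 x 27 = 16.2, taken as 16 true positives and 11 false negatives. The plan states no specificity or PPV, so there is no figure of its own to reproduce.

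**Assumptions.** All 90 have surgery. Of the 63 pathology-negative patients, 13 are PET-positive (TN = 50), or alternatively 6 (TN = 57). U nodes are retained, of which b are benign and definitively followed.

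**Direction.** Specificity = TN/(TN + FP) and PPV = TP/(TP + FP). Losing b benign patients replaces FP by FP - b, so neither measure can fall. NPV and sensitivity contain no FP term and do not move. Losing diseased patients leaves specificity unchanged and lowers PPV and sensitivity. With both kinds lost, PPV can go either way: from TP 16, FP 6, TN 57, losing 1 benign and 3 diseased patients takes PPV from 16/22 = 72.7% to 13/18 = 72.2%, while specificity rises from 57/63 = 90.5% to 57/62 = 91.9%.

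**All retained nodes benign and definitively followed (U = b).** The plan's specificity is TN/(63 - U); with these patients counted as false positives it is TN/63.

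| PET-positive of 63 | U | Specificity, counted | Specificity, plan | Excess (points) | PPV, counted | PPV, plan | Excess (points) |
|---|---|---|---|---|---|---|---|
| 13 | 1 | 50/63 = 79.4% | 50/62 = 80.6% | 1.3 | 16/29 = 55.2% | 16/28 = 57.1% | 2.0 |
| 13 | 2 | 79.4% | 50/61 = 82.0% | 2.6 | 55.2% | 16/27 = 59.3% | 4.1 |
| 13 | 3 | 79.4% | 50/60 = 83.3% | 4.0 | 55.2% | 16/26 = 61.5% | 6.4 |
| 6 | 1 | 57/63 = 90.5% | 57/62 = 91.9% | 1.5 | 16/22 = 72.7% | 16/21 = 76.2% | 3.5 |

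Larger retained shares are unlikely given Section 10.3a. For completeness, 3 of 6 would give 4.5 points (specificity) and 11.5 (PPV), and 6 of 13 would give 8.4 and 14.4. For scale, the 95% Wilson interval for 50/63 is 67.8% to 87.5%.

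**Mixed case, 13 PET-positive, 3 retained: one confirmed diseased, one confirmed benign, one without definitive follow-up.**

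- Plan: TP = 17, FP = 10. Specificity 50/60 = 83.3%, PPV 17/27 = 63.0%.
- Benign patient scored as a false positive: specificity 50/61 = 82.0%, PPV 17/28 = 60.7%. The gap itself is worth 1.4 and 2.2 points.
- Then counting the b.v.1 patient as a false positive gives 50/62 = 80.6% and 17/29 = 58.6%; as a true positive, 50/61 = 82.0% and 18/29 = 62.1%. This further movement comes from non-evaluability, not from the missing rule.

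**Opposite direction.** If 3 retained nodes are all diseased and none is followed, specificity stays at 50/60 = 83.3%, PPV is reported as 16/26 = 61.5% instead of 19/29 = 65.5%, and sensitivity as 16/27 = 59.3% instead of 19/30 = 63.3%.

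**The case against.** Four points on the other side have force.

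1. **A reader might infer that an unremoved node can never count against PET.** The text does not support that. Rule b.iii.1 turns on the node being absent from later imaging, not on its having been excised. A retained node that later disappears can literally meet it. Since b.i.2.a expects treated diseased nodes to shrink and the rescan has no set time, even a diseased node that vanishes under treatment could be scored false positive: specificity would be 50/63 = 79.4% instead of 50/62 = 80.6%. The point is therefore limited to nodes shown to be still present.

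2. **The patient may have a category.** Because only a disease criterion is defined, b.v.1 could be read as covering anything that fails to meet it. The benign case is then non-evaluable rather than unclassified. This is a fair reading, but the patient still leaves the 2x2 table, so the effect on specificity and PPV is the same.

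3. **Definitive follow-up may be uncommon.** The study calendar (Section 7) lists no follow-up imaging, and Section 10.3c leaves further scans and biopsies to the treating physician. The tabulated figures apply only where every retained benign node is definitively followed. Others would stay under b.v.1, a disclosed category, even with a better rule.

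4. **Numbers should be low.** Section 10.3a supports this, and the shift for one to three nodes is small beside the Wilson interval. That limits the size of the error but does not supply the missing rule.

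**Conclusion.** The gap is real and touches two of the four primary measures. For a PET-positive node shown to persist in a pathology-negative patient, the rules allow a result in PET's favour and none against it. Taken alone, this leaves specificity unchanged or overstated, and overstates PPV when the lost patients are benign.

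A reader might go further and infer a large bias, or one that always favours PET. Neither follows. The numbers retained, the share definitively followed and PET specificity are all absent from the documents. Diseased patients lost to b.v.1 pull PPV and sensitivity down, and the vanished-node case acts against PET. On the assumptions shown, a few definitively benign retained nodes are worth about 1 to 4 points of specificity and 2 to 6 of PPV. The plan states no specificity or PPV target, so no stated success decision depends on this. It should be fixed before analysis; the missing rule is clear from the text, while the size remains illustrative.

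**What to change.** 1. Add rule b.iii.2: PET-positive, pathology-negative, node not removed, definitive benign follow-up = false positive. Define benign before analysis, alongside b.i.2.a, as a negative biopsy where one was done, or imaging in the plan's own 3-12 month window that meets a stated benign criterion. Keep indeterminate or absent follow-up under b.v.1. Assign a missing or inconclusive rescan to non-evaluable as well, since b.v.1 now requires imaging that shows the node was left behind.
2. Report the number of b.v.1 patients, and give specificity, PPV and sensitivity with all of them counted as false positive and then all as true positive. Report the b.v.2 patients separately and outside these bounds, because they had no prostatectomy.
3. Optionally, report the four measures against pathology alone, the comparator named in Section 10.1.1, as a sensitivity analysis, noting that pathology did not examine retained nodes.

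The cost is one rule with its criterion and some extra tabulation, using follow-up that b.i.2 already relies on. Specificity and PPV may come out slightly less favourable.

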## **10. MEASUREMENTS**

### **10.1 Study Endpoints**

#### **10.1.1 Primary endpoint:**

- i. Sensitivity, specificity, positive and negative predictive value of  $^{68}\text{Ga}$ -RM2 PET for the detection of regional nodal metastases compared to pathology at radical prostatectomy on a per patient basis.

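### Distant PET findings can decide who gets the reference standard, and unoperated men then leave the primary accuracy analysis with no bounds and no stated scope

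*Combined protocol and SAP*

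**What the plan says.** - **Entry (3.1).** Every man has a prostatectomy with node dissection planned, so at enrolment all are due to receive the reference standard.
- **Primary endpoint (10.1.1).** Sensitivity, specificity and predictive values of "PET for the detection of regional nodal metastases compared to pathology at radical prostatectomy on a per patient basis".
- **Follow-up (10.3a).** Men with no PET-positive nodal or metastatic disease go to surgery, and so do men with a PET-positive regional pelvic node.
- **Follow-up (10.3b).** When PET shows osseous or distant lesions, the urologist is told and more imaging or a targeted biopsy follows, "in order to restage the patient prior to the decision regarding whether or not a prostatectomy will be performed".
- **Classification (10.4b).** Each definition of true positive, true negative, false positive and false negative requires pathology from prostatectomy. Rule b.v.2 adds: "Patients with extrapelvic nodal metastases will not be included in this analysis if patients do not undergo prostatectomy". No rule covers men left unoperated because of bone or visceral lesions, or for any other reason.
- **Size (10.4a).** "Sample size: 90 patients in total". The plan gives no expected number of unoperated men, no allowance for them, no alternative reference for them and no sensitivity analysis.

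**The concern.** The scan under study helps to decide who receives the test that judges it, and those who do not receive it are left out. This is partial verification. A two-by-two table of the verified men does not correct it, because those missing are not a random sample with respect to the PET result.

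At stake is what the four primary figures describe. The stated objective concerns men scheduled for surgery at the time of the scan. As the plan stands, the figures describe men who were still operated on after the scan was read, and nothing in section 10.4 tells the reader so.

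**Working it through.** **Inputs from 10.4a.** 90 patients; "30% of intermediate to high-risk patients have nodal metastases at prostatectomy"; "PET has a 60% detection sensitivity for nodal metastases on a per patient basis"; conventional imaging 45%.

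**Assumptions, not in the documents.** The number and type of men lost; nodal specificity (90% as the working value, 81% to 95% as the range).

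**The plan's own figure.** The 90 cannot be reproduced, because no significance level, power or test is given. At an assumed 5% alpha and 80% power, the smallest requirement among independent, paired and one-sample comparisons is 134 (one-sided McNemar test, minimum discordance 0.15). This point uses 90 only as the number scanned.

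**Step 1: full verification.**
- Node-positive: 90 × 0.30 = 27. True positives: 27 × 0.60 = 16.2. False negatives: 10.8.
- Node-negative: 63. At 90% specificity: 56.7 true negatives and 6.3 false positives.
- PPV = 16.2/22.5 = 72.0%. NPV = 56.7/67.5 = 84.0%.

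**Step 2: k true positives not operated on.** Sensitivity = (16.2 − k)/(27 − k).
- k = 2: 14.2/25 = 56.8%; PPV 14.2/20.5 = 69.3%.
- k = 4: 12.2/23 = 53.0%; PPV 12.2/18.5 = 65.9%.
- Specificity and NPV do not move.

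**Step 3: m node-positive, regionally PET-negative men not operated on** (they had distant uptake). Sensitivity = 16.2/(27 − m).
- m = 3: 16.2/24 = 67.5%; NPV 56.7/64.5 = 87.9%.
- Specificity and PPV do not move.

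**Step 4: a random fraction f of regional PET positives lost.** Sensitivity = 16.2(1 − f)/[16.2(1 − f) + 10.8]. Specificity = 56.7/[56.7 + 6.3(1 − f)].
- f = 10%: sensitivity 14.58/25.38 = 57.4%; specificity 56.7/62.37 = 90.9%.
- f = 20%: sensitivity 12.96/23.76 = 54.5%; specificity 56.7/61.74 = 91.8%.
- PPV stays at 72.0% and NPV at 84.0%.
- For f = 20%, starting specificities of 81% and 95% become 84.2% and 96.0%.

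**Step 5: comparison with conventional imaging.** It detects 27 × 0.45 = 12.15 men, a planned gap of 15 points. With k = 4, PET is at 53.0%, and the gap depends on how the four lost men read on conventional imaging:
- all positive: 8.15/23 = 35.4%, gap 17.6 points;
- an average mix: 10.35/23 = 45.0%, gap 8.0 points;
- all negative: 12.15/23 = 52.8%, gap 0.2 points.

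**The case against.** **The endpoint is defined against prostatectomy pathology, and the exclusion is written in advance.** This stands. A pathology-only estimate is legitimate and should stay primary. What is missing is its stated scope, a rule for all unoperated men, and a range.

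**The route is narrow.** A reader might infer that PET-positive men in general are kept from surgery. Section 10.3a says otherwise for men positive only in regional nodes. Under the written rules a man is lost only if he has distant uptake and surgery is then cancelled after restaging. The background section also says that bone metastases are seldom found at initial staging, although it names small retroperitoneal nodes as part of the problem. Large losses are therefore not supported. Nor do the documents show that the lost men carry the heaviest nodal disease.

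**The 30% refers to findings at prostatectomy, so it may already describe operated men.** This is a fair reading. Suppose 90 men are operated on and the lost men come on top of them. Sensitivity among all scanned men is then 18.2/29 = 62.8% with 2 extra true positives, 20.2/31 = 65.2% with 4, and 16.2/30 = 54.0% with 3 extra false negatives, against 60% reported. The gaps are a little smaller, and the uncertainty of direction remains.

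**Sampling error is larger.** For 16/27 the exact 95% interval is 39% to 78%. The illustrated shifts lie well inside it, but that interval makes no allowance for selection.

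**The plan might seem to hold a substitute reference already.** It does not. The 10.3b work-up is aimed at distant lesions. The criteria in b.i.2.a need a size change on imaging at 3 to 12 months and define only a positive node in men who are regionally PET-positive. For unoperated men they could add true positives and no other class, which would push sensitivity up.

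**Conclusion.** The concern holds in a limited form. Followed as written, the plan gives complete-case accuracy in a partly PET-selected subset, with no bounds and no statement of whom the result describes.

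The size is unknown because the documents give no number of cancelled operations. With the assumed losses shown, expected sensitivity moves from 60% to 56.8% or 53.0% (2 or 4 true positives lost), or to 67.5% (3 false negatives lost). PPV and NPV need not move: random loss among regional PET positives leaves both unchanged.

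A reader might infer that losing about 7 true positives brings PET down to the 45% of conventional imaging, since (16.2 − k)/(27 − k) = 0.45 at k = 7.4. That reading is not supported. It removes men from PET while holding the comparator fixed, and it supposes that over 40% of the true positives have surgery cancelled. As step 5 shows, the gap can narrow or widen.

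**What to change.** 1. Reword b.v.2 to cover every scanned patient without prostatectomy, whatever the reason (nodal, osseous or visceral findings, or other).
2. Add a patient-flow table giving the number and reason by regional PET result.
3. Keep the pathology-only estimate as primary and state that it applies to operated patients.
4. Pre-specify a sensitivity analysis over all scanned patients with best-case and worst-case bounds. Let a, b, c and d be the verified true positives, false positives, false negatives and true negatives. Let u and v be the unverified men who are regionally PET-positive and PET-negative. The bounds are:
   - sensitivity: a/(a + c + v) to (a + u)/(a + u + c);
   - specificity: d/(d + b + u) to (d + v)/(d + v + b);
   - PPV: a/(a + b + u) to (a + u)/(a + b + u);
   - NPV: d/(c + d + v) to (d + v)/(c + d + v).
5. Report any regional-node biopsy or imaging that happens to exist for unoperated men descriptively. Do not use the b.i.2.a criteria as their reference standard.

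The operated men whom b.v.1 leaves unresolved are also unverified and can be counted in u.

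The cost is SAP wording, one table and one extra analysis, with no new procedures and no change to clinical management. The downside is width. With u = 4 and v = 0 after the k = 4 loss in step 2, sensitivity is reported as 53.0% to 60.0%, and specificity (assumed 90%) as 56.7/67.0 = 84.6% to 90.0%.

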## 11. ADVERSE EVENTS AND REPORTING PROCEDURES

### 11.1 Potential Adverse Events

The administration of the radioactive substance will feel like a slight pinprick when given by i.v. injection. Patients who are claustrophobic may feel some anxiety while positioned in the

scanner. Also, some patients find it uncomfortable to hold one position for more than a few minutes. The subjects will not feel anything related to the radioactivity of the substance in their body. Because the radioactivity is very short-lived, the radiation exposure is low. The substance amount is so small that it does not affect the normal processes of the body.

This research study involves exposure to radiation. This radiation exposure is for research purposes only. The amount of radiation from one  $^{68}\text{Ga}$ -RM2 PET is 4.76 mSv, approximately equal to 10% of the limit that radiation workers (for example, a hospital x-ray technician) are allowed to receive in one year. There is no radiation exposure from MRI. Therefore, the total radiation exposure is 4.76 mSv. This amount of radiation involves minimal risk and is necessary to obtain the research information desired.

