## 2.2 Study Design

This is a prospective, single center, single-arm study enrolling 90 participants with intermediate and high-risk prostate cancer. Eligible participants will undergo baseline assessments at enrollment. Study participants will receive  $^{68}\text{Ga}$ -RM2 and undergo a PET/MRI scan. All patients will first be seen by a Stanford Cancer Institute physician and then referred if appropriate on clinical grounds to [name] or his colleagues for this study. The following steps will take place.

1. After signed the informed consent document, participants will be given a copy of the signed form
2. Participant will be asked to drink 1 to 2 glasses of water before arrival at the clinic
3. Participants will be weighed and vital signs (heart rate and blood pressure) will be recorded
4. Study personnel (eg, technologist) will verify subject identity; radiopharmaceutical identity; dose; and administration route. Participant will be injected IV with  $140 \text{ MBq} \pm 20\%$  of  $^{68}\text{Ga}$ -RM2
5. Participant will void immediately prior to the scan
6. Approximately 50 to 100 minutes after the radiopharmaceutical IV administration, data acquisition will begin in the pelvic region and move toward the head. First, localizer MRI scans will be performed to define the table positions. After correct positioning of the spatial acquisition windows is ensured, the combined PET/MRI acquisition will be initiated with 3 to 5 table positions at a 4-min acquisition time per table position.
7. Vital signs (heart rate and blood pressure) will be recorded again at the completion of the study.
8. Participants will be dismissed.
9. Participants will be contacted at 24 to 72 hours following the scan in order to capture potential late occurring Adverse Events.

The  $^{68}\text{Ga}$ -RM2 PET/MRI may be repeated at the completion of treatment to evaluate response to therapy, if requested by the treating physician.

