### **4. IMAGING AGENT INFORMATION**

#### **4.1 Study Agent**

We will use Ga-RM2 as the PET radiopharmaceutical. The administered dosage is 140 MBq ± 20% i.v.

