## 7. STUDY CALENDAR

	Pre-Study	Week 1	24 - 72 Hours Post-Study	12 Months
Informed consent	X			
Demographics	X			
Medical history	X			
Follow-up Call to Participant			X	
 Ga-RM2 PET/MRI		X		
Data analysis				X

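### Section 11.1 gives the total research exposure as one scan (4.76 mSv), but sections 2.2 and 10.3 permit repeat 68Ga-RM2 scans, so the total is too low for anyone who has one

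*Combined protocol and SAP*

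**What the plan says.** Section 11.1 says the exposure from one 68Ga-RM2 "PET is 4.76 mSv, approximately equal to 10% of the limit that radiation workers" may receive in a year. It adds "This radiation exposure is for research purposes only" and then gives the total: "There is no radiation exposure from MRI. Therefore, the total radiation exposure is 4.76 mSv". The sentence that follows calls this amount minimal risk. Nothing limits the total to participants who are scanned once.

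Two other sections allow more than one administration:

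- Section 2.2, after its numbered steps, says the 68Ga-RM2 "PET/MRI may be repeated at the completion of treatment to evaluate response to therapy, if requested by the treating physician".
- Section 10.3a.i says that patients with nodes seen on PET but "without positive nodes on pathology, will be rescanned with MRI or CT to determine if the suspicious node was thought to be removed". It adds that a 68Ga-RM2 "PET may be repeated as well".

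The section 7 calendar has one PET/MRI, in Week 1, and one row for "Follow-up Call to Participant", marked at 24 to 72 hours. It has no entry for a repeat scan or a post-operative rescan. Step 9 of section 2.2 ties the 24 to 72 hour contact to the scan, in the singular.

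**The concern.** The total in section 11.1 holds only for a participant who has one administration and no study-driven CT. The protocol itself opens paths on which that is not so. The figure supports the minimal-risk statement, so an understated total understates what a re-dosed participant may receive under the study.

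There is a related gap in safety follow-up. The vital signs and late adverse-event contact in section 2.2 belong to a sequence written around one scan. A reader cannot tell whether they apply after a second dose of the investigational agent. None of this touches the diagnostic-accuracy analysis; the issue is the risk statement and the consistency of the schedule.

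**Working it through.** **Inputs from the documents**

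- Exposure per scan: 4.76 mSv, about 10% of an annual worker limit (section 11.1). The limit is not stated; 4.76 / 0.10 implies 47.6 mSv.
- Activity: "The administered dosage is 140 MBq ± 20% i.v" (section 4.1), which is 112 to 168 MBq.
- Cited dosimetry (section 2.1): 0.051 mSv/MBq; also 7.7 mSv for 150 MBq, or 5.7 mSv with frequent bladder voiding, which gives 5.7 / 150 = 0.038 mSv/MBq.
- Permitted repeats: one option in section 2.2 and one in section 10.3a.i, with no maximum in either.

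**Step 1. The plan's own total.** Total = number of administrations × exposure per scan + MRI contribution = 1 × 4.76 + 0 = 4.76 mSv. The sum is correct for one scan. The gap is in what it covers.

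**Step 2. The total with repeats, on the protocol's per-scan figure.**

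- Two administrations: 2 × 4.76 = 9.52 mSv.
- Three administrations (baseline and both repeat options as separate scans): 3 × 4.76 = 14.28 mSv.

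**Step 3. Can the per-scan figure be reproduced?**

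- 140 × 0.051 = 7.14 mSv (112 to 168 MBq: 5.71 to 8.57 mSv), which is 50% above 4.76.
- 140 × 0.038 = 5.32 mSv (4.26 to 6.38 mSv), which is 12% above 4.76.
- 4.76 / 140 = 0.034 mSv/MBq, a coefficient that the documents do not give.

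At the nominal activity, neither cited coefficient yields 4.76. The totals for one, two and three administrations would then be:

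| Per-scan basis | One | Two | Three |
|---|---|---|---|
| Section 11.1 figure (4.76 mSv) | 4.76 | 9.52 | 14.28 |
| 0.038 mSv/MBq at 140 MBq | 5.32 | 10.64 | 15.96 |
| 0.051 mSv/MBq at 140 MBq | 7.14 | 14.28 | 21.42 |

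On every basis, a second administration doubles the one-scan total.

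**Step 4. The rescan.** Section 10.3a.i accepts MRI or CT, and section 11.1 counts MRI as zero. This path therefore adds exposure only if CT is chosen or the PET is repeated. The documents give no CT dose, so no figure can be attached. They also do not say whether such a CT counts as research exposure, although section 10.4 uses the post-operative imaging to classify patients for the accuracy analysis.

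**Step 5. The schedule.** The calendar has one scan and one call. Step 9 of section 2.2 is not expressly limited to the baseline scan, and does not expressly extend to a repeat.

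**The case against.** The strongest reply is that section 11.1 labels its figure as coming from one PET, that the arithmetic is right for one PET, and that repeats are optional. All of that is true, but the concluding sentence is an unqualified total, and the optional scans are written into this protocol and use its investigational agent.

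Several stronger readings are tempting, and the documents do not support them:

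- **That everyone sent for the post-operative rescan exceeds 4.76 mSv.** A participant rescanned only by MRI stays at 4.76 mSv on the protocol's own account.
- **That 14.28 mSv is the protocol's maximum.** It is one scenario. The planned treatment is prostatectomy, so one scan after surgery might serve both repeat provisions. With no stated maximum, three administrations is not a ceiling either.
- **That exposure reaches 20% or 30% of the worker limit.** 9.52 / 47.6 = 20% and 14.28 / 47.6 = 30%, but the limit is annual, the repeats have no fixed date, and the study runs 48 months. The percentages hold only if all scans fall within one year.
- **That the number affected can be estimated.** The documents give no nodal specificity for 68Ga-RM2. Any count of PET-positive, pathology-negative patients would rest on an assumed value, and would measure entry to an MRI-or-CT path rather than extra radiation. The section 2.2 repeat depends on a request from the treating physician.
- **That repeat doses have no safety follow-up.** Step 9 of section 2.2 can be read to cover a repeat. Adverse-event reporting in section 8 and committee review of serious events in section 9.2 are not limited to the first dose.

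**Conclusion.** The point holds for repeat 68Ga-RM2 administrations. Section 11.1 presents a one-scan exposure as the study total, while sections 2.2 and 10.3a.i permit more scans without a maximum. For a participant re-dosed once, the protocol's own figure gives 9.52 mSv, twice the stated total; using both options as separate scans gives 14.28 mSv, three times. These totals take 4.76 mSv per scan as given. The figure needs confirming, because the dosimetry cited in section 2.1 gives 7.14 mSv at 140 MBq, or 5.32 mSv with frequent voiding. A dosimetry source that the protocol does not cite could account for the difference.

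The number of participants affected is unknown, and any CT contribution cannot be quantified from the documents. On safety follow-up, the supportable conclusion is an ambiguity: the calendar omits repeats, and step 9 of section 2.2 does not say whether it covers them.

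**What to change.** Reconcile sections 2.1, 2.2, 4.1, 7, 10.3a.i and 11.1.

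1. Confirm the per-scan exposure and cite the source of its coefficient.
2. Either label 4.76 mSv (or the confirmed value) as exposure per scan, or restate the total for the number of administrations that the protocol permits. If a percentage of the worker limit is kept, state the limit and the time frame.
3. Say whether a CT used for the section 10.3a.i rescan, or for the follow-up imaging in section 10.4, counts as research exposure. If so, include its dose.
4. State whether the vital signs and the 24 to 72 hour contact in section 2.2 apply to repeat administrations, and make the calendar match.
5. Check that the minimal-risk statement still rests on the restated figure.

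How many repeats to permit, and what monitoring follows them, is the sponsor's decision. The cost is a text amendment and a less favourable stated exposure.
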